### 14.6.3. Efficacy

Daily eDiary endpoints																								
General																								
Participants were instructed to complete the daily eDiary in the evening (typically at bedtime). The parameters collected include rescue use and EXACT-PRO scores.																								
The tables below show which daily eDiary records are used to calculate the daily eDiary parameters for each period. Any diary data collected after the minimum of (Day 168 and the day before study treatment stop date) will not be slotted.																								
To be used for rescue use endpoints and E-RS: COPD total and subscale scores:																								

  
 Period	First day	Last day	
   
 Baseline	Latest of (7 days before Study treatment start date (Day 1) and day of Visit 1 (Screening))	Day before Day 1 of study treatment	
 
 Month 1	Study day 1	Study day 28	
 
 Month 2	Study day 29	Study day 56	
 
 Month 3	Study day 57	Study day 84	
 
 Month 4	Study day 85	Study day 112	
 
 Month 5	Study day 113	Study day 140	
 
 Month 6	Study day 141	Earliest of (Study day 168 and day before study treatment stop date)	
  
	Period	First day	Last day	Baseline 	Latest of (7 days before Study treatment start date (Day 1) and day of Visit 1 (Screening))	Day before Day 1 of study treatment	Month 1 	Study day 1	Study day 28	Month 2 	Study day 29	Study day 56	Month 3 	Study day 57	Study day 84	Month 4 	Study day 85	Study day 112	Month 5 	Study day 113	Study day 140	Month 6 	Study day 141	Earliest of (Study day 168 and day before study treatment stop date)
Period	First day	Last day																						
Baseline 	Latest of (7 days before Study treatment start date (Day 1) and day of Visit 1 (Screening))	Day before Day 1 of study treatment																						
Month 1 	Study day 1	Study day 28																						
Month 2 	Study day 29	Study day 56																						
Month 3 	Study day 57	Study day 84																						
Month 4 	Study day 85	Study day 112																						
Month 5 	Study day 113	Study day 140																						
Month 6 	Study day 141	Earliest of (Study day 168 and day before study treatment stop date)																						
[1] The denominator for baseline and monthly mean scores is the number of days with a non-missing score; this is also used to determine whether or not a baseline (≥4 days) or monthly mean (≥10 days) is calculated.																								
EXACT PRO																								

 
• The EXACT-PRO (Evidera, 2016a) is a 14-item daily diary (typically completed at bedtime)
 
• The daily E-RS: COPD total score (and subscales) will be computed according to the E-RS in COPD user manual (Evidera, 2016b).
 
• The monthly mean for E-RS: COPD total score, and the subscale scores RS-Breathlessness, RS-Cough and Sputum, and RS-Chest Symptoms will be calculated as the mean of the daily scores in the monthly intervals defined above.
 
• Mean monthly score = (sum of daily scores/# diary days completed).
 
• A participant must have at least 10 days of diary data in any month to contribute a non-missing monthly mean of daily values; otherwise the monthly mean for that month will be considered missing.
 
• A participant must have at least 4 days of diary data in the 7 days prior to treatment start date to contribute a non-missing mean of daily values for baseline; otherwise baseline will be considered missing.
 
• If missing values occur for individual items, the E-RS: COPD total score and E-RS: COPD subscale
 
																								

Daily eDiary endpoints
 
score that contain the item will be set to missing on that day.


Responders according to E-RS: COPD Total and Subscale Scores
 
 
• A participant will be considered as a responder according to E-RS: COPD total score if their monthly mean change from baseline E-RS: COPD total score <math>\leq -2.0</math>.
 
• A participant will be considered as a non-responder according to E-RS: COPD total score if their monthly mean change from baseline E-RS: COPD total score <math>>-2.0</math>.
 
• A participant will be considered as a responder according to E-RS: COPD breathlessness score if their month mean change from baseline E-RS: COPD breathlessness score <math>\leq -1.0</math>.
 
• A participant will be considered as a non-responder according to E-RS: COPD breathlessness score if their monthly mean change from baseline E-RS: COPD breathlessness score <math>>-1.0</math>.
 
• A participant will be considered as a responder according to E-RS: COPD cough & sputum score if their monthly mean change from baseline E-RS: COPD cough & sputum score <math>\leq -0.70</math>.
 
• A participant will be considered as a non-responder according to E-RS: COPD cough & sputum score if their monthly mean change from baseline E-RS: COPD cough & sputum score <math>>-0.70</math>.
 
• A participant will be considered as a responder according to E-RS: COPD chest symptoms score if their monthly mean change from baseline E-RS: COPD chest symptoms score <math>\leq -0.70</math>.
 
• A participant will be considered as a non-responder according to E-RS: COPD chest symptoms score if their monthly mean change from baseline E-RS: COPD chest symptoms score <math>>-0.70</math>.
 
• If the monthly mean E-RS: COPD score is missing then response status will be missing.
 


Season
 
 
• For each participant and each month, season will be assigned based on the first date with a non-missing daily score in the monthly mean E-RS: COPD total score.
 
• Australia will add 6 months to the first day of the monthly mean E-RS: COPD total score before season is assigned.
 
• If the month of the first day of the monthly mean score period is:             
 
▪ Dec, Jan or Feb then season is Winter
 
▪ Mar, Apr or May then season is Spring
 
▪ Jun, Jul or Aug then season is Summer
 
▪ Sep, Oct or Nov then season is Fall
 
 
 

Mean Number of Rescue Puffs per Day and Percentage Rescue Free Days
 
 
• If a participant has more than one daily diary record for any given day, the worst case response on that day for each endpoint will be used in the summaries and analyses. i.e. the maximum number of puffs of rescue use reported will be counted for the day in question and used to determine if it was a rescue-free day.
 
• A rescue-free day is defined as a day where the total puffs is 0.
 
• For each summary period, the mean number of puffs per day and the percentage of rescue free days, will be calculated, using the number of days with non-missing values for the endpoint as denominator.
 
• Rescue use will be summarized over the periods defined above.
 

HCRU Exacerbations
Duration

 
The duration of the exacerbation will be calculated as (exacerbation resolution date or date of death - exacerbation onset date + 1).
 

Severity

 
Each HCRU exacerbation will be categorized based on severity as follows:                             
 
Mild: no treatment with oral/systemic corticosteroids and/or antibiotics and not involving hospitalisation, an emergency room visit or resulting in death
 
Moderate: required treatment with oral/systemic corticosteroids and/or antibiotics (not involving hospitalisation, an emergency room visit or resulting in death).
 
Severe: required in-patient hospitalization, an emergency room visit, or resulted in death
 
 
 

Time to First Exacerbation

 
The time to first on-treatment Moderate/Severe HCRU exacerbation will be calculated as exacerbation onset date of first on-treatment moderate or severe on-treatment exacerbation – date of start of treatment +1
 
Participants will be represented from their treatment start date to their first on-treatment moderate or severe exacerbation or date of censoring.
 
For the strategic interim analysis, participants that have not experienced an on-treatment exacerbation are censored at the earliest of (treatment stop date + 3, date of death, or the interim cut-off date, 1AUG2018).
 
For the final analysis, participants that have not experienced an on-treatment exacerbation are censored at the earliest of (treatment stop date + 3, date of death, date of exclusion from the per protocol population (if analysis is in Per Protocol population))
 

Raw Annual Rate

 
Raw annual rate is the event rate per 1000 participant-years, calculated as the number of events x 1000, divided by the total duration at risk (minimum(treatment stop date + 1, date of death, date of exclusion from the per protocol population (if analysis is in Per Protocol population)) – treatment start date + 1).
 

Offset Variable

 
For analyses of exacerbation rate, the offset variable will be defined as the logarithm of the ((minimum (date of end of study treatment + 3, date of death, date of exclusion from the per protocol population (if analysis is in Per Protocol population)) – date of start of treatment + 1)/365.25)
 

EXACT Events
General

 
The daily EXACT-PRO scores will be computed according to the EXACT-PRO user manual (Evidera, 2016a) and used to identify EXACT-defined events, including the frequency, duration and severity of the events.
 
Events will be categorized as recovered, censored, or persistent worsening (according to the manual).
 

Time to First Event

 
The time to first on-treatment EXACT event will be calculated as the onset date of the first on-treatment EXACT event – date of start of treatment +1
 
Participants will be represented from their treatment start date to their first EXACT event or date of censoring.
 
For the final analysis, participants that have not experienced an EXACT event are censored at the earliest of (Day 168, treatment stop date - 1, date of death, or date of final EXACT-PRO assessment, date of exclusion from the per protocol population (if analysis is in Per Protocol population))
 

Raw Annual Rate

 
Raw annual rate is the event rate per 1000 participant-years, calculated as the total number of EXACT-defined events x 1000, divided by the total duration at risk (minimum(Day 168, treatment stop date - 1, date of death, date of final EXACT-PRO assessment, date of exclusion from the per protocol population (if analysis is in Per Protocol population)) – treatment start date + 1).
 

Offset Variable

 
For analyses of EXACT event rate, the offset variable will be defined as the logarithm of the ((minimum (Day 168, treatment stop date - 1, date of death, date of final EXACT-PRO assessment, date of exclusion from the per protocol population (if analysis is in Per Protocol population)) – date of start of treatment + 1)/365.25)
 

CAT
CAT Score

 
The CAT consists of eight items each formatted as a six-point differential scale: 0 (no impact) to 5 (high impact). A CAT score will be calculated by summing the non-missing scores on the eight items. The score can have values ranging from 0 to 40.
 
If one item is missing, then the score for that item is set as the average of the non-missing items. If more than one item is missing, then the CAT score will be set to missing.
 
If the language of the CAT conducted at a post-baseline visit is different to the language used at baseline, the CAT score for that visit and all subsequent visits will be set to missing.
 
If there is more than one response to a question at a visit or duplicate questionnaires, the CAT score for that visit will be set to missing.
 

Responders according to CAT Score

 
A participant will be considered as a responder according to CAT score if their change from baseline CAT score <math>\leq -2.0</math>.
 
A participant will be considered as a non-responder according to CAT score if their change from baseline CAT score <math>> -2.0</math>.
 
If CAT score is missing at a visit, the response status will be missing at that visit.
 

Season

 
For each participant and each visit, season will be assigned based on visit date.
 
Australia will add 6 months to the visit date before season is assigned.
 
If the month of the visit is:             
 
Dec, Jan or Feb then season is Winter
 
Mar, Apr or May then season is Spring
 
Jun, Jul or Aug then season is Summer
 
Sep, Oct or Nov then season is Fall
 
 
 

SGRQ
SGRQ Domain and Total Scores

 
The SGRQ-C contains 14 questions with a total of 40 items grouped into three domains (Symptoms, Activity and Impacts).
 
Details for how to score the SGRQ-C, including handling of missing data or multiple responses to questions, are outlined in the SGRQ-C manual (Jones, 2016).
 
SGRQ-C domains and total scores will be converted to SGRQ scores as described in the manual.
 
Changes from baseline in domain and total score will be calculated for the converted scores.
 
If the language of the SGRQ-C conducted at a post-baseline visit is different to the language used at baseline, all SGRQ scores at that visit and all subsequent visits will be set to missing.
 

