**7.2.1.2. Summary Measure**

Rate ratio (also expressed as percentage rate reduction) for each danirixin dose vs. placebo

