**Summary Results Presentation**

For HCRU exacerbations:

- Number and percent of participants reporting an exacerbation (mild, moderate, severe and moderate/severe), number and percent of participants with each number of moderate/severe exacerbations (0, 1,  $\geq 2$ ), the total number of exacerbations per treatment and annual raw exacerbation rate (as defined in Section 14.6.3). This table will be repeated for HCRU exacerbations that were treated with Antibiotics and will include the number and percentage of participants who were receiving ICS treatment at the time of the exacerbation.
- For each moderate/severe exacerbation, the outcome, severity, duration, whether the exacerbation led to hospitalization, systemic/oral corticosteroids being taken, antibiotics being taken, or emergency room visit.

For EXACT events:

- Number and percent of participants reporting an EXACT-defined event, number and percent of

participants with each number of EXACT-defined events (0, 1,  $\geq 2$ ), the number of EXACT-defined events and annual raw event rate (as defined in Section 14.6.3) will be summarized for all events and for recovered, censored and persistent worsening events separately for each treatment group. The duration and severity (indicated by the maximum observed value and duration) will be reported for all events.

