**14.4.1.3. Study Phases for Event Data**

Classification of a HCRU exacerbation/AE as having onset on-treatment will be made with reference to the study treatment start and stop dates and the event onset date. If the event onset date is missing, then the event will be considered on-treatment.

Study Phase	Definition
Pre-treatment	If onset date is prior to treatment start date Start Date < Study Treatment Start Date
On-treatment	If onset date is on or after treatment start date & on or before treatment stop date + 3. Study Treatment Start Date ≤ Start Date ≤ Study Treatment Stop Date + 3 days
Post-treatment	If onset date is after treatment stop date + 3. Start Date > Study Treatment Stop Date + 3 days

Note: assume on-treatment unless there is evidence to the contrary

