**CONFIDENTIAL**

205724

Efficacy: Tables						
StInt No.	SAC No.	Population	IDSL / Example Shell	Title	Programming Notes	Deliverable [Priority]
2.14		PP		Analysis of Change from Baseline Monthly Mean E-RS: COPD Total Score up to Month 6 by Baseline E-RS: COPD Total Score (<10, >=10)	Frequentist MMRM Endpoints: E-RS: COPD total score	StInt
2.15	2.9	PP		Analysis of Change from Baseline Monthly Mean E-RS: COPD Total Score up to Month 6 by Smoking Status at Screening (Current, Former)	Frequentist MMRM Endpoints: E-RS: COPD total score	StInt, SAC
2.16		PP		Analysis of Change from Baseline Monthly Mean E-RS: COPD Total Score up to Month 6 by Country	Frequentist MMRM Endpoints: E-RS: COPD total score	StInt
2.17	2.10	PP		Analysis of Change from Baseline Monthly Mean E-RS: COPD Total Score up to Month 6 by % Predicted FEV1 at Screening (<50, >=50)	Frequentist MMRM Endpoints: E-RS: COPD total score	StInt, SAC
2.18	2.11	PP		Analysis of Change from Baseline Monthly Mean E-RS: COPD Total Score up to Month 6 by Baseline CAT Score (<10, >=10)	Frequentist MMRM Endpoints: E-RS: COPD total score	StInt, SAC
2.19		PP		Analysis of Change from Baseline Monthly Mean E-RS: COPD Total Score up to Month 6 by Exacerbation History (>=2 moderate/severe vs. 1 moderate/severe, prior year)	Frequentist MMRM Endpoints: E-RS: COPD total score	StInt
2.20		PP		Analysis of Change from Baseline Monthly Mean E-RS: COPD Total Score up to Month 6 by COPD Medication Grouping at Baseline (ICS+LABA+LAMA, ICS+LABA, LABA+LAMA, Other)	Frequentist MMRM Endpoints: E-RS: COPD total score	StInt

Efficacy: Tables						
StInt No.	SAC No.	Population	IDSL / Example Shell	Title	Programming Notes	Deliverable [Priority]
2.21		PP		Analysis of Change from Baseline Monthly Mean E-RS: COPD Total Score up to Month 6 by CMH Status at Baseline	Frequentist MMRM Endpoints: E-RS: COPD total score	StInt
2.22		PP		Analysis of Change from Baseline Monthly Mean E-RS: COPD Total Score up to Month 6 by Season	Frequentist MMRM Endpoints: E-RS: COPD total score	StInt
	2.12			Summary of Responders to E-RS: COPD Total Score, SGRQ and CAT at Month 6	Include categories for E-RS, SGRQ, CAT, E-RS+SGRQ, E-RS+CAT, SGRQ+CAT, E-RS+SGRQ+CAT, None, Missing	Post SAC
Exacerbations						
2.23	2.13	PP		Summary of On-treatment HCRU Exacerbations		StInt, SAC
	2.14	PP		Summary of On-treatment Details of Moderate/Severe HCRU Exacerbations		SAC

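### The HCRU raw annual rate ends time at risk two days before its event window closes, and neither the HCRU nor the EXACT raw-rate formula converts days to years

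*SAP*

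**What the plan says.** SAP 14.6.3 (HCRU Exacerbations, Raw Annual Rate) labels the rate per 1000 participant-years and defines it as "calculated as the number of events x 1000, divided by the total duration at risk (minimum(treatment stop date + 1, date of death". The date of exclusion from the per protocol (PP) population follows as a further limit, after which treatment start date is subtracted and 1 added.

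Three other HCRU definitions end the period three days after stopping:

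- SAP 14.4.1.3 classes an exacerbation as on-treatment if onset is "on or before treatment stop date + 3".
- SAP 14.6.3, Time to First Exacerbation: in the final analysis, event-free participants are "censored at the earliest of (treatment stop date + 3, date of death, date of exclusion from the per protocol population".
- SAP 14.6.3, Offset Variable: the model offset uses "minimum (date of end of study treatment + 3, date of death", with the PP exclusion date as a further limit, and divides the resulting days by 365.25.

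For EXACT events, SAP 14.6.3 gives the raw rate, again labelled per 1000 participant-years, as "calculated as the total number of EXACT-defined events x 1000, divided by the total duration at risk". Its end of risk is the earliest of Day 168, stop date -1, death, final EXACT-PRO assessment and PP exclusion. The EXACT offset and censoring rule use the same limits, and the offset divides by 365.25.

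The HCRU raw rate appears in SAC Table 2.13, "Summary of On-treatment HCRU Exacerbations". SAP 7.2.1.5.1 adds a second version, SAC Table 2.15: "This table will be repeated for HCRU exacerbations that were treated with Antibiotics". The EXACT raw rate appears in SAC Table 2.19.

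**The concern.** A crude rate needs its numerator and denominator to cover the same period. The HCRU numerator runs to stop date +3 and the denominator to stop date +1, so the rate is biased upwards. The SAP gives no reason for the difference.

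The second problem is the unit. The label promises events per 1000 participant-years, but the HCRU and EXACT formulas divide by a count of days. The label and the formula give different numbers, and nothing in the raw-rate entry says which governs.

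The stakes are limited to the descriptive tables. The raw rate is the plain counterpart of the model-estimated rate reported for each arm, and a reader will expect the two to rest on the same time at risk. The endpoint's summary measure is "Rate ratio (also expressed as percentage rate reduction) for each danirixin dose vs. placebo", which comes from the model and does not use the raw rate.

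**Working it through.** The documents state no numerical rate, so there is no figure of the plan's own to reproduce. The formulas are evaluated as written.

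**Inputs.** Treatment lasts 24 weeks, i.e. 168 days (SAP 2.3). Planned dropout is about 10% (Protocol 5.2). The end points of risk and event time are those in SAP 14.4.1.3 and 14.6.3. Assumed, not in the documents: a constant event rate, dropout uniform over Days 1 to 168, 30% dropout as an upper case, and the event rates and counts below.

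**Window, per participant.** Let T = stop date - start date + 1.

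- Raw-rate time at risk = T + 1 days.
- Event window and offset time = T + 3 days.
- Overstatement = (T + 3)/(T + 1) - 1.

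| Stop day | Raw-rate days | Event-window days | Overstatement |
|---|---|---|---|
| 168 | 169 | 171 | 1.18% |
| 84 | 85 | 87 | 2.4% |
| 28 | 29 | 31 | 6.9% |

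**Window, per arm.** The crude rate pools days, so mean T is used. Dropouts have mean T = (1 + 168)/2 = 84.5.

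- 10% dropout: mean T = 0.9 × 168 + 0.1 × 84.5 = 159.65; 162.65/160.65 - 1 = 1.24%.
- 30% dropout: mean T = 0.7 × 168 + 0.3 × 84.5 = 142.95; 145.95/143.95 - 1 = 1.39%.
- Arm with 30% dropout against arm with none: 1.01389/1.01183 - 1 = 0.20%.

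**Unit, HCRU.** Take 100 participants who all stop on Day 168, with an assumed true rate of 1.0 per participant-year.

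- Expected events = 100 × 171/365.25 = 46.8.
- Correct rate = 46.8 × 1000/(100 × 171/365.25) = 1000.
- Stop +1 kept, /365.25 supplied = 46.8 × 1000/(100 × 169/365.25) = 1012.
- Formula coded literally = 46.8 × 1000/(100 × 169) = 2.8.

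For assumed true rates of 0.5 to 1.5, these become 500 to 1500, 506 to 1518, and 1.4 to 4.2.

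**Unit, EXACT.** A stop on Day 168 gives 167 days at risk. With an assumed 50 events in 100 such participants, the literal formula gives 50 × 1000/(100 × 167) = 2.99, and dividing the days by 365.25 gives 1093.6. For 25 to 100 events the results are 1.50 to 5.99 and 546.8 to 2187.1. The ratio is always 365.25. The EXACT window needs no correction.

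**The case against.** The best case against the unit point is that the intended calculation can be recovered. The label fixes the unit, the adjacent offset supplies 365.25, and a literal result near 3 would look absurd beside the model-estimated rates once these were put on the same scale. This largely stands: the factor of 365.25 is a worst case, not the expected outcome. The formula as written still does not yield its stated unit.

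On the window, the error is about 1%, nearly the same in every arm, and touches no inference. That stands in full.

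A further point is that PP exclusion may end risk before either +1 or +3 applies. Under final-analysis criterion 10 in SAP Appendix 1, participants off study medication for more than 14 days leave the PP analyses from the day they stopped. The text does not settle whether this covers permanent discontinuation. If it does, and the exclusion date equals the stop date, dropouts contribute T days to both periods:

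- 10% dropout: (0.9 × 171 + 0.1 × 84.5)/(0.9 × 169 + 0.1 × 84.5) - 1 = 162.35/160.55 - 1 = 1.12%.
- 30% dropout: (0.7 × 171 + 0.3 × 84.5)/(0.7 × 169 + 0.3 × 84.5) - 1 = 145.05/143.65 - 1 = 0.97%.

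The larger early-stopper figures would then not arise, but completers keep the 1.18% error and the arm-level error stays near 1%.

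The text is not superseded: SAP 1.1 lists the raw annual rate and offset among the definitions that the amendment clarified.

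**Conclusion.** The concern holds, as a minor correction. The HCRU raw rate is wrong as defined: about 1.2% too high where the stop date ends time at risk, and about 1.0% to 1.4% per arm across the dropout levels and readings of criterion 10 considered. These figures assume a constant event rate and uniform dropout; the 30% level is also an assumption. Differential dropout of 30% against 0% would distort the comparison of crude rates by only about 0.2%.

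The HCRU and EXACT raw-rate formulas both lack the conversion that their label requires. The consequence ranges from none to a factor of 365.25, depending on how they are coded. Because both offsets have the right window and unit, the modelled rates, rate ratios and credible intervals are unaffected.

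**What to change.** In SAP 14.6.3, define the HCRU duration at risk as (minimum(treatment stop date + 3, date of death, date of PP exclusion if applicable) - treatment start date + 1)/365.25, which is the exponentiated offset. Add /365.25 to the EXACT raw-rate denominator and leave its window unchanged.

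This costs two lines of text and the matching program lines for SAC Tables 2.13, 2.15 and 2.19. It needs no new data and changes no model.
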